3. SUMMARY OF STUDY PLAN

This is a single center, double-blind, randomized, placebo-controlled, pilot study. The goal of this Phase I trial is to determine the safety of Berberine in subjects with UC in clinical remission and maintained with Mesalamine. Pilot information about Berberine's ability to modulate relevant biomarkers at the dose being assessed will also be gathered.

Subjects will be randomized in a double-blind fashion to 300 mg TID Berberine (12 subjects) versus placebo (4 subjects), for 3 months. Two additional participants are anticipated to be accrued (for a total of 18 subjects) to account for an anticipated dropout rate of 10%. In order to keep the numbers in either treatment group as planned, dropouts in either treatment group will be replaced by subjects assigned to that same treatment and gender group. Assuming an accrual rate of approximately 1.5 per month, we expect the study to be completed in 12 months.

Subjects will be enrolled and followed up at Department of Gastroenterology, Xijing Hospital, Xi'an, China. For those subjects experiencing grade 2 toxicity felt to be due to Berberine, the dosage will be successively decreased by 100 mg decrements per dose until resolution (note, given TID dosing, this translates to 300 mg/day decrements). Those not tolerating 300 mg/day, will be removed from study, as will those experiencing grade 3 or 4 toxicity at any dose. Compliance will be assessed by pill counts and diary reviews at monthly clinical visits and by measuring plasma Berberine concentrations at the end of the trial. Subjects whose compliance is below 80% will be removed from study.

Colorectal biopsies and blood samples will be taken at the initial visit (pre-treatment). At the end of the 3-month treatment, subjects will repeat earlier screening assessments to determine the outcomes of the primary and secondary objectives. One month post study, subjects will be contacted by clinical visit to assess symptoms.

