7. CLINICAL EVALUATIONS AND PROCEDURES

7.1 Schedule of Events

Evaluation/ Procedure	Screening	Randomization	Day 0*	Day 7 (+/- 3 days)	Day 30 (+/- 3 days)	Day 60 (+/- 7 days)	Day 90 (- 7 days)	Day 120 (+/- 7 days) or Early Termination
Informed Consent	X							
Assess Eligibility	X	X						
Medical History	X							
Physical Exam	X			X	X	X	X	
Vital Signs, Height and Weight ¹	X			X	X	X		X
Baseline Symptoms	X							
UCDAI Questionnaire	X					X		
Laboratory Tests ²	X					X		
Rectal Biopsy ³	X					X		
Research Blood Collection ⁴	X					X		
Concomitant Medications	X		X	X	X	X	X	X
Dispense Study Agent		X		X	X			
Pill Count				X	X	X	X	
Review Agent Diary/Record				X	X	X	X	
Adverse Events			X	X	X	X	X	X
Telephone Contact ⁵			X	X				
Collect Study Agent						X		

1. Vital signs assessment is to include pulse, blood pressure, respiration rate, temperature and weight. Baseline assessment must also include height.
2. CBC, ESR, CRP, and Chemistry Panel (White blood count, RBC count, Hemoglobin, Hct, Platelets, Absolute Neutrophil Count, Glucose, Creatinine, Sodium, Potassium, Chloride, SGOT, SGPT, Total Bilirubin, INR). Baseline assessment must include a serum pregnancy test for all women of childbearing potential. Pregnancy test will only be performed at the screening visit.
3. Colonoscopy with 7 biopsies from inflammatory loci (or from regions close to the initial inflammatory area when the patient was first diagnosed). Biopsies taken on day 90 should be ≥ 5 cm distance from the original biopsy sites.
4. Research blood collection: 5ml into purple EDTA tube for plasma and 4ml into red top tube for cytokines.
5. For Day 0, either a telephone contact or an office visit will occur.

* Participant should begin taking the study medication within 7 days of the screening visit

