7.2 Baseline Testing/Prestudy Evaluation

Screening

- Informed Consent – written informed consent must be obtained prior to any other study procedure. Participants' signature is required on the research informed consent (in addition to the procedure consent) prior to undergoing the screening colonoscopy.
- Participants will be told not to take Berberine for 3 days prior to the screening biopsy.
- Medical History and Baseline Symptom Review.
- Concomitant Medication Review – all medications that the participant has taken within the 3 months prior to consent are to be recorded.
- Physical Exam and Vital Signs assessment – vital signs assessment is to include pulse, blood pressure, respiration rate, temperature and weight. Baseline assessment must also include height.
- UCDAI questionnaire to help assess disease state.
- Inclusion / Exclusion Criteria Review.
- Clinical Lab Tests (27-31 ml blood) CBC, ESR, CRP and Chemistry Panel (White blood count, RBC count, Hemoglobin, Hct, Platelets, Absolute Neutrophil Count, Glucose, Creatinine, Sodium, Potassium, Chloride, SGOT, SGPT, Total Bilirubin). Baseline assessment must include an INR for all patients and a serum pregnancy test for all women of childbearing potential. Women of childbearing potential include those who have not been surgically sterilized and have had a period in the past year. Screening labs must be completed within two weeks of registration.
- Research blood will be collected: Peripheral blood for cytokines analysis (4ml in red top tube) and plasma for Berberine concentration analysis (5ml in purple EDTA tube).
- Colonoscopy with 7 biopsies from inflammatory loci (or from regions close to the initial inflammatory area when the patient was first diagnosed). Each biopsy site will be recorded by denoting the length in centimeters from the anal verge to the biopsy site as well as recording position of the participant during time of biopsy (e.g., lying on their left side).
- Register the patient with Northwestern University Clinical Research Office.
- Provide agent diary (Appendix D) and review it with participant.

Randomization

- Confirm that the patient meets all inclusion/exclusion criteria.
- Randomize the patient with Northwestern University Clinical Research Office.
- Participant will be asked to return to the clinic within 6 days of the screening visit to pick up the study medication. Three (3) bottles 100mg x 120# Berberine tablets/placebo for use as medication will be dispensed.

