7.3 Evaluation During Study Intervention

Day 0

- Telephone contact or office visit with participant with instructions to begin study agent and diary completion.

- Participants should begin taking the study medication within 7 days of the screening visit.
- Assess Adverse Events
- Assess Concomitant Medications

Day 7 (+/- 3 days)

- Telephone contact with participant
- Assess study drug compliance
- Assess adverse events and discuss patient diary
- Assess Concomitant Medications

Day 30 (+/- 3 days)

- Physical Exam and Vital Signs assessment – vital signs assessment is to include pulse, blood pressure, respiration rate, temperature and weight.
- Assess study drug compliance
- Assess adverse events and discuss patient diary
- Assess Concomitant Medications
- Dispense 3 bottles 100mg x 120# Berberine tablets/placebo for use as medication.

Day 60 (+/- 7 days)

- Physical Exam and Vital Signs assessment – vital signs assessment is to include pulse, blood pressure, respiration rate, temperature and weight.
- Assess study drug compliance
- Assess adverse events and discuss patient diary
- Assess Concomitant Medications
- Dispense 3 bottles 100mg x 120# Berberine tablets/placebo for use as medication.

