8. CRITERIA FOR EVALUATION AND ENDPOINT DEFINITION

8.1 Primary Endpoint

Safety will be measured at study visits using the NCI Common Terminology Criteria for Adverse Events (CTCAE) v4 and recorded in case report forms. In addition to assessing clinical toxicity, we will collect tissue and blood samples from recruited participants at the beginning of the trial and at the end of Berberine administration (three months later) and evaluate organ toxicity by standard clinical chemistry tests. Finally, we will observe and record symptoms such as fever, fatigue, weight loss, appetite, stool frequency, bloody stool and other upper and lower gastrointestinal tract symptoms in participants.

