13.4 Primary Objective, Endpoint(s), Analysis Plan

Primary Objective: To determine the safety of Berberine administered to patients with UC in clinical remission while receiving maintenance therapy with Mesalamine.

Endpoints: The primary objective will be evaluated by determining whether given subject experiences grade 2 systemic toxicity or not. Upon unblinding the placebo and treatment assignments, relevant counts and rates will be evaluated and reported. Specifically, in addition to assessing clinical toxicity, we will collect tissue and blood samples from recruited participants at the beginning of the trial and at the end of Berberine administration (three months later) and evaluate organ toxicity by standard clinical chemistry tests. Also, we will read tissue samples in China and the US. Finally, we will observe and record symptoms such as fever, fatigue, weight loss, appetite, stool frequency, bloody stool and other upper and lower gastrointestinal tract symptoms in participants.

Analysis: We plan to recruit 12 treatment and 4 placebo subjects for a total of 16 evaluable subjects. With potential dropout of 2 subjects we plan to recruit a total of 18 subjects. Dropouts in either treatment group will be replaced by subjects assigned to that same treatment and gender group. We do not expect to see any toxicity in either group of

patients; in fact we believe the underlying toxicity rate is the same in both groups. With no observed toxicities, we will be able to establish an approximate 95% upper bound on Prob(Tox) as the “Rule of Three”: $3/(n+1)$ or $3/17 = 0.18$ for both groups and $3/13 = 0.23$ for the treatment group⁴³. Other statistical analysis will consist of providing descriptive statistics (mean, SD, max, min) on patient characteristics and on toxicity rates; in case no events occur, appropriate methods will be used, such as the Rule of Three above for upper confidence bound, continuity correction or exact confidence bounds for two-sided intervals.

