APPENDIX D

Patient Diary

DAY __	DAY __	DAY __	DAY __	DAY __	DAY __	DAY __	
DATE: ___/___/___	DATE: ___/___/___	DATE: ___/___/___	DATE: ___/___/___	DATE: ___/___/___	DATE: ___/___/___	DATE: ___/___/___	
MORNING DOSE	MORNING DOSE	MORNING DOSE	MORNING DOSE	MORNING DOSE	MORNING DOSE	MORNING DOSE	
Time ___ : ___	Time ___ : ___	Time ___ : ___	Time ___ : ___	Time ___ : ___	Time ___ : ___	Time ___ : ___	
 Not taken	 Not taken	 Not taken	 Not taken	 Not taken	 Not taken	 Not taken	
MID-DAY DOSE	MID-DAY DOSE	MID-DAY DOSE	MID-DAY DOSE	MID-DAY DOSE	MID-DAY DOSE	MID-DAY DOSE	
Time ___ : ___	Time ___ : ___	Time ___ : ___	Time ___ : ___	Time ___ : ___	Time ___ : ___	Time ___ : ___	
 Not taken	 Not taken	 Not taken	 Not taken	 Not taken	 Not taken	 Not taken	
EVENING DOSE	EVENING DOSE	EVENING DOSE	EVENING DOSE	EVENING DOSE	EVENING DOSE	EVENING DOSE	
Time ___ : ___	Time ___ : ___	Time ___ : ___	Time ___ : ___	Time ___ : ___	Time ___ : ___	Time ___ : ___	
 Not taken	 Not taken	 Not taken	 Not taken	 Not taken	 Not taken	 Not taken	
Please list any new symptoms or reasons for missed doses:		Please list any new symptoms or reasons for missed doses:		Please list any new symptoms or reasons for missed doses:		Please list any new symptoms or reasons for missed doses:	
<hr/> <hr/> <hr/> <hr/> <hr/>		<hr/> <hr/> <hr/> <hr/> <hr/>		<hr/> <hr/> <hr/> <hr/> <hr/>		<hr/> <hr/> <hr/> <hr/> <hr/>	

[Page left blank due to formatting]

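### The listed symptoms belong to the primary safety evaluation, but after screening fatigue, appetite and most GI symptoms have no structured repeat measure, and the diary asks only about new ones

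*Combined protocol and SAP*

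**What the plan says.** Section 8.1 defines the primary endpoint as safety graded by CTCAE and adds that "we will observe and record symptoms such as fever, fatigue, weight loss, appetite, stool frequency, bloody stool", together with other upper and lower gastrointestinal symptoms. Sections 2.3 and 13.4 repeat the list. The per-participant measure in 13.4 is "whether given subject experiences grade 2 systemic toxicity or not". No toxicity is expected, and 13.4 gives approximate 95% upper bounds for zero events of 0.18 (16 participants) and 0.23 (12 on Berberine).

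Section 3 states that at the end of treatment "subjects will repeat earlier screening assessments to determine the outcomes of the primary and secondary objectives", and then: "One month post study, subjects will be contacted by clinical visit to assess symptoms".

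In Section 7.1 the only symptom row is "Baseline Symptoms", marked at screening. Section 7.2 has the matching entry, "Medical History and Baseline Symptom Review". Sections 7.3 to 7.5 name no symptom review. Their relevant entry at Days 7, 30, 60 and 120 is "Assess adverse events and discuss patient diary", with near-identical wording at Day 90. The diary in Appendix D prompts: "Please list any new symptoms or reasons for missed doses".

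**The concern.** A symptom that counts towards the primary evaluation should be asked about in the same way before and during treatment. Here a review is named at baseline and not again, so later information on several listed symptoms depends on what a participant volunteers or what an open question happens to draw out. The diary narrows this further: someone who enters with mild abdominal discomfort that becomes worse has no new symptom to write down.

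Two things are at stake. The planned headline is an upper bound from zero events in a very small group, so a single missed or under-graded event changes it materially. And Section 6.8 says the placebo arm is there to help judge faint, sub-clinical effects of taking part. Open questioning is weakly suited to that, and without a like-for-like measure there is no change from baseline to compare between arms.

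**Working it through.** **Coverage of each symptom.** The columns of the schedule are displaced in the text available to me, so I took timings from Sections 7.2 to 7.5.

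| Symptom | Source at screening | Structured source after screening |
|---|---|---|
| Fever | Temperature | Temperature, Days 30, 60, 90, 120 |
| Weight loss | Weight | Weight, Days 30, 60, 90, 120 |
| Stool frequency | UCDAI | UCDAI, Day 90 only |
| Bloody stool | UCDAI | UCDAI, Day 90 only |
| Fatigue | Symptom review (content not stated) | None named |
| Appetite | Symptom review (content not stated) | None named |
| Other GI symptoms | Symptom review (content not stated) | None named |

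Adverse events of any kind are also queried at Days 0, 7, 30, 60, 90 and 120.

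The last row matters most. Section 6.2 reports mild to moderate constipation in 3–8% of subjects and, in another study, 3 of 61 patients stopping for abdominal pain, rash or constipation. The UCDAI stool item (Appendix A) scores only stools above the patient's normal number, so constipation scores 0. Abdominal discomfort enters only through the physician's global item. Toxicity is evaluated from first dose to Day 120 (Section 13.7), while the on-treatment UCDAI is a single reading at Day 90.

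**The plan's bounds.** With zero events, the rule 3/(n+1) gives:
- n = 16: 3/17 = 0.1765, stated as 0.18.
- n = 12: 3/13 = 0.2308, stated as 0.23.

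Both reproduce. The exact one-sided 95% bound, 1 − 0.05^(1/n), is 0.1707 and 0.2209, so the stated figures are slightly conservative.

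**Dependence on capture.** Suppose a participant with a true grade 2 toxicity is recorded as such with probability s. Zero recorded events then bounds p × s, and the bound on p is the exact bound divided by s. It passes the stated figure when s falls below:
- n = 12: 0.2209/0.23 = about 0.96.
- n = 16: 0.1707/0.18 = about 0.95.

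The documents give no value for s, so this shows how little slack there is and does not estimate any shortfall.

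**One event instead of none.** This needs no capture rate. With one event, the exact one-sided 95% upper bound solves (1−p)^n + n·p·(1−p)^(n−1) = 0.05:
- n = 12: p = 0.3387 (check: 0.0070 + 0.0430 = 0.0500). The bound moves from 0.22 to 0.34, a factor of 0.3387/0.2209 = 1.53.
- n = 16: p = 0.2640 (check: 0.0074 + 0.0425 = 0.0499, which is 0.05 up to rounding). The bound moves from 0.17 to 0.26, a factor of 0.2640/0.1707 = 1.55.

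**The case against.** The best defence is that a baseline reference followed by adverse-event recording is a coherent design. Section 11 counts any unfavourable symptom as an adverse event whether or not related, 11.1 requires all of them to be recorded with a CTCAE grade, and nothing there excludes worsening of an existing symptom. Six contacts are scheduled, and 4.4 has adverse events assessed at each contact. Four of the six symptoms named in 8.1 have the same measure at screening and Day 90. Grade 2 events, which involve intervention or limits on daily activities, are harder to miss than mild ones. The case report forms are in Appendix E, which is not among the documents, so they may carry prompts not visible here.

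Most of this stands, and it rules out three stronger readings:
- A reader might infer that on-treatment symptoms rest on adverse-event questioning and the diary alone. The vital signs and the Day 90 UCDAI show otherwise.
- A reader might infer that the toxicity bound is too favourable. The bounds reproduce, they concern grade 2 toxicity, and no capture rate is given from which an error could be calculated.
- A reader might infer that 7.1 to 7.5 flatly contradict Section 3. The end-of-treatment sentence there does not name symptoms, and the Day 120 visit, with its examination and adverse-event assessment, can be read as the promised symptom contact.

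The defence does not reach fatigue, appetite or other GI symptoms. For these the plan names no repeated measure. The adverse-event definition permits recording a worsened symptom, but no procedure shown asks about it, and the data elements in 11.1.2 include no baseline grade.

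**Conclusion.** The point holds as a gap in measurement. The listed symptoms are part of the primary safety evaluation, but a symptom review is named only at screening, and the toxicities most to be expected from Section 6.2 are among those without a like-for-like measure afterwards. Section 13.4 also specifies no tabulation of the symptoms it lists.

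The bounds of 0.18 and 0.23 are arithmetically right and conditional on complete capture of grade 2 events. They may be optimistic if events are missed; the size of any shortfall cannot be derived. The shift from 0.22 to 0.34 shows how much one event matters among 12. It is not a claim that one will be missed. The conclusion assumes that the visit lists in 7.2 to 7.5 are complete and that the unseen case report forms do not already repeat a symptom checklist.

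**What to change.** - **7.1 to 7.5:** use one symptom review, built on the 8.1 list plus constipation and abdominal pain, with a CTCAE grade for each item, at screening and at Days 30, 60, 90 and 120/Early Termination. Section 7.2 does not say what the present baseline review contains, so the same items should be specified there too.
- **Appendix D:** change the diary prompt to ask for *new or worse symptoms*.
- **13.4:** tabulate worst grade and change from baseline for each symptom by arm, and say that the zero-event bounds assume complete capture of grade 2 events.

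If the sponsor prefers not to add the review, the minimum is to state in 8.1 how each listed symptom is captured after baseline.

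The cost is a short form and a few minutes at visits already planned, with no new visit or procedure. More mild events will be recorded, so the overall adverse-event profile may look less favourable. Grade 1 events do not enter the grade 2 measure or its bound.

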7.2 Baseline Testing/Prestudy Evaluation

Screening

- Informed Consent – written informed consent must be obtained prior to any other study procedure. Participants' signature is required on the research informed consent (in addition to the procedure consent) prior to undergoing the screening colonoscopy.
- Participants will be told not to take Berberine for 3 days prior to the screening biopsy.
- Medical History and Baseline Symptom Review.
- Concomitant Medication Review – all medications that the participant has taken within the 3 months prior to consent are to be recorded.
- Physical Exam and Vital Signs assessment – vital signs assessment is to include pulse, blood pressure, respiration rate, temperature and weight. Baseline assessment must also include height.
- UCDAI questionnaire to help assess disease state.
- Inclusion / Exclusion Criteria Review.
- Clinical Lab Tests (27-31 ml blood) CBC, ESR, CRP and Chemistry Panel (White blood count, RBC count, Hemoglobin, Hct, Platelets, Absolute Neutrophil Count, Glucose, Creatinine, Sodium, Potassium, Chloride, SGOT, SGPT, Total Bilirubin). Baseline assessment must include an INR for all patients and a serum pregnancy test for all women of childbearing potential. Women of childbearing potential include those who have not been surgically sterilized and have had a period in the past year. Screening labs must be completed within two weeks of registration.
- Research blood will be collected: Peripheral blood for cytokines analysis (4ml in red top tube) and plasma for Berberine concentration analysis (5ml in purple EDTA tube).
- Colonoscopy with 7 biopsies from inflammatory loci (or from regions close to the initial inflammatory area when the patient was first diagnosed). Each biopsy site will be recorded by denoting the length in centimeters from the anal verge to the biopsy site as well as recording position of the participant during time of biopsy (e.g., lying on their left side).
- Register the patient with Northwestern University Clinical Research Office.
- Provide agent diary (Appendix D) and review it with participant.

Randomization

- Confirm that the patient meets all inclusion/exclusion criteria.
- Randomize the patient with Northwestern University Clinical Research Office.
- Participant will be asked to return to the clinic within 6 days of the screening visit to pick up the study medication. Three (3) bottles 100mg x 120# Berberine tablets/placebo for use as medication will be dispensed.
- If participant is unable to return to the clinic within 6 days, the study medication will be shipped to their home.

7.3 Evaluation During Study Intervention

Day 0

- Telephone contact or office visit with participant with instructions to begin study agent and diary completion.

- Participants should begin taking the study medication within 7 days of the screening visit.
- Assess Adverse Events
- Assess Concomitant Medications

Day 7 (+/- 3 days)

- Telephone contact with participant
- Assess study drug compliance
- Assess adverse events and discuss patient diary
- Assess Concomitant Medications

Day 30 (+/- 3 days)

- Physical Exam and Vital Signs assessment – vital signs assessment is to include pulse, blood pressure, respiration rate, temperature and weight.
- Assess study drug compliance
- Assess adverse events and discuss patient diary
- Assess Concomitant Medications
- Dispense 3 bottles 100mg x 120# Berberine tablets/placebo for use as medication.

Day 60 (+/- 7 days)

- Physical Exam and Vital Signs assessment – vital signs assessment is to include pulse, blood pressure, respiration rate, temperature and weight.
- Assess study drug compliance
- Assess adverse events and discuss patient diary
- Assess Concomitant Medications
- Dispense 3 bottles 100mg x 120# Berberine tablets/placebo for use as medication.

